2.7 Safety analyses

Safety analyses will be based on the safety set unless otherwise specified. The summary tables will be presented for 'Responders', 'Non-responders' and 'All subjects' where indicated. Listings will be provided.

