6.1.5 Treatment duration

The planned duration of treatment with eltrombopag is 6 months.

The planned duration of treatment with cyclosporine is 6 months for non-responders and up to 24 months for responders who do not relapse prior to 6 months. Patients who relapse prior to 24 months will discontinue cyclosporine and study, and will be followed-up for 30 days.

For patients who meet any toxicity criteria, the investigator must follow the guideline on dose reduction and/or discontinuation presented in [Section 6.3](#). Patients can remain on study treatment until toxicity or withdrawal of consent, refer to [Sections 7.1.5](#) and [7.1.6](#).

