The reference start date for all assessments (safety, efficacy, patient reported outcomes (PROs), etc.) will be the start date of study treatment.

The study day will be displayed in the data listings. If an event starts before the reference start date, the study day displayed in the listing will be negative.

Baseline

Baseline is the result of an investigation describing the “true” uninfluenced state of the patient, defined as the period from the date of signing any informed consent document to the start date of study treatment. Assessments, specified to be collected post-dose on the first date of study treatment are not considered.

The last non-missing assessment, including unscheduled assessments on or before the date of start of study treatment is defined as “baseline value” or “baseline assessment”.

Where multiple measurements meet the baseline definition, with no further flag or label that can identify the chronological order, then values from central assessments should be considered as baseline rather than local values.

For electrocardiogram (ECG) parameters, if there are multiple replicates per time point, the average of these measurements would be calculated for baseline (if not already available in the database).

If patients have no value as defined above, the baseline result will be missing.

Observation periods

The overall observation period will be divided into three mutually exclusive segments:

1. **Pre-treatment:** from day of patient’s informed consent to start date of study treatment
2. **On-treatment:** from start date study treatment to last date of study treatment + 30 days
3. **Post-treatment:** from last date of study treatment + 31 days

On-treatment assessments/events

The definition of on-treatment is given below, depending on the context.

For safety summary tables an on-treatment AE is defined as any AE reported in the following time interval (including the lower and upper limits):

- <date of first administration of study treatment; date of last administration of study treatment + 30 days>

This corresponds to the definition of treatment-emergent AEs given in the protocol, i.e. AEs which are newly reported or worsening from baseline.

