An on-treatment assessment is defined as any assessment performed after the date of first administration of study treatment (except for assessments specified to be collected post-dose on that day), i.e. assessments performed in the following time interval (including the lower and upper limits):

- <date of first administration of study treatment + 1; date of last administration of study treatment + 30 days>

For patients whose last date of study treatment is missing, on-treatment assessments/events include any assessment/event present in the database occurring after the start date of study treatment.

Listings will contain all data, flagging assessments/events outside of the on-treatment period where applicable.

Definition of Months and Years

A month will be calculated as $(365.25 / 12) = 30.4375$ days. If duration is to be reported in months, duration in days will be divided by 30.4375. If duration is to be reported in years, duration in days will be divided by 365.25.

Time since initial SAA diagnosis

Time since initial SAA diagnosis (days) = First dose date (Epag/CsA) – date of initial diagnosis.

Time windows

Time windows for assessments are based on protocol specified windows. Weekly and biweekly visits should be completed ± 1 day. Biweekly visits after 6 months should be completed ± 2 days. Monthly visits should be completed ± 3 days. Bimonthly visits should be completed ± 1 week.

Time windows for multiple assessments

In order to summarise data of assessments collected over time (including any unscheduled visits), the assessments will be time slotted. If more than one assessment is done within the same time window, the assessment performed closest to the target date will be used. If 2 assessments within a time window are equidistant from the target date, then the earlier of the 2 assessments will be used. If multiple assessments on the same date then the worst case will be used. The end of treatment assessment will be included if collected within 30 days of the last treatment date. Data from all assessments (scheduled and unscheduled), including multiple assessments, will be listed.

Last contact date

The last contact date will be derived for patients not known to have died at the analysis cut-off date using the latest complete date among the following:

Table 2-1 Last contact date data sources

Source data	Conditions
Date of withdrawal of consent	Withdrawal of study informed consent

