2.5.1 Primary endpoint

The overall hematologic response rate (ORR) is defined as the proportion of patients achieving complete response (CR) and partial response (PR) defined as follows:

Partial response (PR) is defined as any two of the following parameters at two consecutive, scheduled visit measurements at least 7 days apart during the first 6 months of study (and not sufficient for CR) and no platelet transfusions within 7 days of platelet measurement (can still be a PR if ANC and reticulocyte measurements are valid):

- Absolute neutrophil count (ANC) $\geq 500/\mu\text{L}$
- Platelet count $\geq 20\,000/\mu\text{L}$
- Reticulocyte count $\geq 60\,000/\mu\text{L}$ (automated)

Complete response (CR) is defined as all three parameters meet the following criteria at two consecutive, scheduled visit measurements at least 7 days apart during the first 6 months of study and no platelet transfusions within 7 days of platelet measurement and no RBC transfusion with 14 days of the hemoglobin measurements:

- ANC $\geq 1\,000/\mu\text{L}$
- Platelet count $\geq 100\,000/\mu\text{L}$
- Hemoglobin $\geq 10\text{ g/dL}$

ORR_6 = Number of patients who achieved hematologic response by 6 months/Number of patients in the FAS.

Responder status: If any patient achieves hematologic response (either CR or PR) any time on or before the 6 months visit, they will be considered a **responder**, else they are a **non-responder**.

The point estimate along with the corresponding exact 95% confidence interval using Clopper and Pearson exact method will be presented for ORR_6.

Day 10 (plat 8 000) sample at 10:00 and platelet transfusion Day 10 11:00 (plat 60 000)—assume transfusion is always after the blood sample Day 10 sample is valid for efficacy.

Day 11 to Day 16 not valid (Day 11 (50 000), 12 (45 000), 13, 14, 15, 16 (transfusion minimal impact by day 7) not valid). Both Day 10 and Day 17 samples are valid for efficacy

Handling of missing values/discontinuations

If any patient achieves overall hematologic response any time before 6 months but discontinues prior to 6 months or has missing parameters required for assessing overall hematologic response at any point after achieving the first response, they will be considered as responders.

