2.7.1 Adverse events (AEs)

The AEs will be coded using the latest version of MedDRA at the time of the analysis. AEs will be graded using the common toxicity criteria for adverse events (CTCAE) Version 4.03

AE summaries will only include AEs during the on-treatment period. A column for 'Grade ≥ 3 ' may be included in the AE tables. If a patient reported more than one AE with the same preferred term (PT), the AE with the greatest severity will be presented. If a patient reported more than one AE within the same primary system organ class (SOC), the patient will be counted only once with the greatest severity at the SOC level, where applicable. An AE with missing CTCAE grade will be included in the 'All grades' column of the summary tables.

In AE summaries, the primary SOC will be presented alphabetically and the PTs will be sorted within the primary SOC in descending frequency.

Summary tables will be provided for:

- Overview of AEs
 - In-text table
- All AEs regardless of relationship to study treatment by primary SOC, PT and maximum severity and age as well as ethnicity
 - In-text table by SOC and maximum severity
 - In-text table by PT and maximum severity
- AEs suspected to be related to study treatment by SOC, PT and maximum severity
 - In-text table by PT and maximum severity
- AEs leading to study treatment discontinuation regardless of relationship to study treatment by SOC, PT and maximum severity
 - In-text table by PT and maximum severity
- AEs leading to study treatment discontinuation suspected to be related to study treatment by SOC, PT and maximum severity
- AEs leading to study treatment adjustment and/or interruption regardless of relationship to study treatment by SOC, PT and maximum severity
- SAEs regardless of relationship to study treatment by SOC, PT and maximum severity
 - In-text table by PT and maximum severity
- SAEs suspected to be related to study treatment by SOC, PT and maximum severity
- On-treatment deaths and SAEs suspected to be related to study treatment by SOC and PT
- Non-SAEs regardless of relationship to study treatment (threshold 0-5%) by SOC and PT
- On-treatment deaths by SOC and PT and age, ethnicity as well as responder status
 - In-text table by SOC and PT
 - All deaths by SOC and PT and responder status

All AEs will be listed. AEs outside of the on-treatment period will be flagged.

Adverse events of special interest / grouping of AEs

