The adverse events of special interest (AESI) are maintained and updated on a regular basis in the project case retrieval sheet (CRS) and the latest version at the time of the analyses will be used. An in-text and post-text summary table by SOC, PT and maximum severity will be provided.

An AESI is a grouping of AEs that are of scientific and medical concern specific to eltrombopag. These groupings are defined using MedDRA terms, standardized MedDRA queries (SMQs), high level group terms (HLGTs), HLT (high level terms) and PTs. Customized SMQs called Novartis MedDRA queries (NMQs) may also be used. A NMQ is a customized group of search terms which defines a medical concept for which there is no official SMQ available or the available SMQ does not completely fit the need. It may include a combination of single terms and/or an existing SMQ, narrow or broad. For each specified AESI, number (%) of patients with at least one event of the AESI occurring during on-treatment period will be summarised by responder status and overall.

A listing of AESIs will be provided and a listing of all grouping levels down to the MedDRA preferred terms used to define each AESI will be generated.

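### AESI and death tables by responder status give crude percentages over about 7 planned months for non-responders and up to about 25 for responders, on a status set after baseline

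*SAP*

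**What the plan says.** SAP 2.7 sets the general rule for the safety tables: "The summary tables will be presented for 'Responders', 'Non-responders' and 'All subjects' where indicated". SAP 2.7.1 then applies the split explicitly in three places. For each AESI, the number and percentage of patients with at least one event "occurring during on-treatment period will be summarised by responder status and overall". One death table reads "On-treatment deaths by SOC and PT and age, ethnicity as well as responder status", and a further table covers all deaths by responder status without the on-treatment limit.

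Responder status comes from SAP 2.5.1: "If any patient achieves hematologic response (either CR or PR) any time on or before the 6 months visit", the patient is a responder; everyone else is a non-responder.

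The windows follow from three rules.
- SAP 2.7.1: "AE summaries will only include AEs during the on-treatment period".
- SAP 2.1.3, for the on-treatment period: "from start date study treatment to last date of study treatment + 30 days".
- Protocol 6.1.5: "The planned duration of treatment with cyclosporine is 6 months for non-responders and up to 24 months for responders who do not relapse" before month 6.

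SAP 1.1 adds that responders who have lost response at month 6 stop then, and that later relapsers stop at relapse. Each group is followed for 30 more days. Eltrombopag ends at month 6 for everyone (Protocol 6.1.1.1).

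For the safety objective, SAP Table 1-1 names two horizons: 6 months, and 24 months for responders only. Section 2.7 does not turn these into tables. It gives no common window and no patient-time rate for the AESI or death splits, and SAP 2.1.1 uses all data up to the cut-off.

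**The concern.** Two features act on these columns.

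First, planned observation is unequal. A percentage with at least one event rises with time watched, so AESIs can look more frequent in responders at the same underlying rate.

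Second, the grouping is made after baseline. A patient has to survive and stay on study long enough to respond, so deaths before response fall into the non-responder column by definition. That is immortal-time bias, and it acts in the opposite direction.

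A reader of the final report will see the columns side by side. Deaths will be read closely, because six fatal cases led to the recruitment hold described in the rationale for protocol amendment 2. With both features in play, neither the AESI columns nor the death columns can be read as a safety difference between responders and non-responders.

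**Working it through.** The plan gives no figure for this point to reproduce, so the check builds the windows from its rules.

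**Planned windows.** Inputs: 24 and 6 months of treatment (Protocol 6.1.5); 30 days after last dose (SAP 2.1.3); and the SAP 2.1.3 conversion, "duration in days will be divided by 30.4375".
- Responders, ceiling: 24 + 30/30.4375 = 24.99 months.
- Non-responders, ceiling: 6 + 30/30.4375 = 6.99 months.
- Ratio: 24.99/6.99 = 3.58.

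**Allowing for early stops.** Let f be the share of responders who stop at month 6 and g the share of the rest who relapse by month 24, at constant hazard k = −ln(1−g)/18. The mean time after month 6 for those who continue is m = g/k (18 if g = 0). Mean window = f × 6.99 + (1−f) × (6 + m + 0.99). Both shares are assumptions.

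| f | g | m (months) | Mean window (months) | Ratio to 6.99 |
|---|---|---|---|---|
| 0 | 0 | 18 | 25.0 | 3.6 |
| 10% | 35% | 14.6 | 20.1 | 2.9 |
| 50% | 50% | 13.0 | 13.5 | 1.9 |

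The 35% borrows the relapse figure that Protocol 2.1 gives for horse ATG with cyclosporine, which is a different regimen.

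**Effect on a crude percentage.** Assume the same constant rate of 3% per month in both groups; incidence = 1 − exp(−0.03 × t).
- Non-responders, t = 6.99: 18.9%.
- Responders, t = 24.99: 52.7%.
- Responders, t = 20.1: 45%.
- Responders, t = 13.5: 33%. Averaging over individual windows instead of using the mean would be slightly lower.

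If the rate drops after the first 6.99 months, for a responder followed to month 24:
- Halved: 1 − exp(−(0.03 × 6.99 + 0.015 × 18)) = 38%.
- Cut to a quarter: 1 − exp(−(0.03 × 6.99 + 0.0075 × 18)) = 29%.

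**Effect of the post-baseline status on deaths.** Assume that death is unrelated to response, 10% die by month 6, and 40% would respond by month 6 if they lived. Hazards per month: death −ln(0.9)/6 = 0.01756; response −ln(0.6)/6 = 0.08514; sum 0.10270. Probability of either event by month 6: 1 − 0.9 × 0.6 = 0.46.
- Responders: 0.08514/0.10270 × 0.46 = 0.381.
- Deaths before response: 0.01756/0.10270 × 0.46 = 0.0787.
- Deaths after response: 0.10 − 0.0787 = 0.0213.
- Six-month deaths: responders 0.0213/0.381 = 5.6%; non-responders 0.0787/0.619 = 12.7%.

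With 5% to 15% mortality and 30% to 50% response, the same formulas give 2.7% to 8.8% in responders against 6.0% to 20.4% in non-responders, a ratio of 2.1 to 2.5.

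**Both effects together.** Keep the death hazard constant and use the planned windows, with no early stops.
- Responders: 1 − 0.9 × 0.4 × exp(−0.01756 × 18.99)/0.381 = 32%.
- Non-responders: 1 − 0.9 × 0.6 × exp(−0.01756 × 0.99)/0.619 = 14%.

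The order reverses. Deaths clustered before response would push it back.

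**The case against.** The strongest reply is that little depends on these columns. The trial has one arm, no test compares safety by responder status, and the column for all subjects carries the safety conclusion. Exposure is summarised (SAP 2.4.1), adverse events and deaths are listed, and listings show study day, so timing can be recovered. This stands in part: the counts are correct and only a side-by-side reading misleads. But a table split by responder status invites that reading.

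The constant-rate figures also sit badly with the design. SAP 2.7.1 defines AESIs as concerns specific to eltrombopag, which stops at month 6, and cyclosporine is reduced from then on. This stands, which is why the falling-rate cases are shown. They shrink the gap without closing it.

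Three stronger readings are tempting, and the documents do not support them.
- A reader might infer that every adverse event table is split. The list in SAP 2.7.1 names responder status only for AESIs and deaths. SAP section 4 adds only relevant adverse events, and the table shells that would settle it are a separate document.
- A reader might take 25 months as the typical responder window. It is a ceiling; the 7 months is likewise a ceiling, for non-responders treated under amendment 2.
- A reader might conclude that deaths will gather in non-responders purely by construction. Protocol 1.1 says infection is most often the cause of death in refractory cytopenias, so a real excess is plausible, and longer follow-up works the other way. The protocol does not say whether the deaths reported by October 2018 came before response.

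**Conclusion.** The concern holds for the tables the SAP commits to: AESIs and deaths by responder status. They combine a status set after baseline, planned windows that differ by a factor of up to 3.6 (1.9 to 3.6 on average under the assumed stop and relapse shares), and crude percentages with no common window or patient-time.

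For AESIs, time alone could give about 33% to 53% in responders against 19%, at an assumed equal and constant 3% per month. A responder followed to month 24 would show 29% to 38% if the rate fell to between a quarter and a half. For deaths, the two biases oppose each other and the net direction cannot be known in advance. For other adverse event tables the point applies only if the shells split them.

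This is a reporting weakness that should be corrected. It does not touch the primary analysis or the column for all subjects.

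**What to change.** **AESI table, and any other adverse event table the shells split by responder status.** Present the split for events in a common window: the first 6 months, plus 30 days for those who stop. This agrees with the 6-month horizon in SAP Table 1-1, although that wording sits next to laboratory changes, so its reach to adverse events is a reading. The ceilings become 6.99 months for those who stop and 6.00 for responders who continue, a ratio of 1.16 instead of 3.58. Running the window to 6.99 months for everyone would make it 1.00. Print patient-time beside the percentages, because some patients stop early.

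**Later period.** Show months 6 to 24 for responders only, in a separate column with patient-time and events per 100 patient-months, not pooled with time on eltrombopag.

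**Deaths by responder status.** Keep all deaths. Show them up to month 6 and after month 6, with patient-time at risk and whether death came before or after first response. Footnote that status is set after baseline and that the columns are not a safety comparison. A month-6 landmark comparison is not suitable: non-responders leave about 1 month later (0.99) against up to 18.99 months for responders, and every earlier death would drop out.

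**All subjects.** Leave as planned.

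**Cost.** SAP wording, a few extra columns and a footnote; the dates are already collected. The common window removes most or all of the difference in planned time. It does not remove the classification bias (5.6% against 12.7% in the worked case), and the report should say so.

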2.7.1 Adverse events (AEs)

The AEs will be coded using the latest version of MedDRA at the time of the analysis. AEs will be graded using the common toxicity criteria for adverse events (CTCAE) Version 4.03

AE summaries will only include AEs during the on-treatment period. A column for 'Grade ≥ 3 ' may be included in the AE tables. If a patient reported more than one AE with the same preferred term (PT), the AE with the greatest severity will be presented. If a patient reported more than one AE within the same primary system organ class (SOC), the patient will be counted only once with the greatest severity at the SOC level, where applicable. An AE with missing CTCAE grade will be included in the 'All grades' column of the summary tables.

In AE summaries, the primary SOC will be presented alphabetically and the PTs will be sorted within the primary SOC in descending frequency.

Summary tables will be provided for:

- Overview of AEs
 - In-text table
- All AEs regardless of relationship to study treatment by primary SOC, PT and maximum severity and age as well as ethnicity
 - In-text table by SOC and maximum severity
 - In-text table by PT and maximum severity
- AEs suspected to be related to study treatment by SOC, PT and maximum severity
 - In-text table by PT and maximum severity
- AEs leading to study treatment discontinuation regardless of relationship to study treatment by SOC, PT and maximum severity
 - In-text table by PT and maximum severity
- AEs leading to study treatment discontinuation suspected to be related to study treatment by SOC, PT and maximum severity
- AEs leading to study treatment adjustment and/or interruption regardless of relationship to study treatment by SOC, PT and maximum severity
- SAEs regardless of relationship to study treatment by SOC, PT and maximum severity
 - In-text table by PT and maximum severity
- SAEs suspected to be related to study treatment by SOC, PT and maximum severity
- On-treatment deaths and SAEs suspected to be related to study treatment by SOC and PT
- Non-SAEs regardless of relationship to study treatment (threshold 0-5%) by SOC and PT
- On-treatment deaths by SOC and PT and age, ethnicity as well as responder status
 - In-text table by SOC and PT
 - All deaths by SOC and PT and responder status

All AEs will be listed. AEs outside of the on-treatment period will be flagged.

Adverse events of special interest / grouping of AEs

The adverse events of special interest (AESI) are maintained and updated on a regular basis in the project case retrieval sheet (CRS) and the latest version at the time of the analyses will be used. An in-text and post-text summary table by SOC, PT and maximum severity will be provided.

An AESI is a grouping of AEs that are of scientific and medical concern specific to eltrombopag. These groupings are defined using MedDRA terms, standardized MedDRA queries (SMQs), high level group terms (HLGTs), HLT (high level terms) and PTs. Customized SMQs called Novartis MedDRA queries (NMQs) may also be used. A NMQ is a customized group of search terms which defines a medical concept for which there is no official SMQ available or the available SMQ does not completely fit the need. It may include a combination of single terms and/or an existing SMQ, narrow or broad. For each specified AESI, number (%) of patients with at least one event of the AESI occurring during on-treatment period will be summarised by responder status and overall.

A listing of AESIs will be provided and a listing of all grouping levels down to the MedDRA preferred terms used to define each AESI will be generated.

